16.1.2. MISSING DATA IMPUTATION METHOD FOR PRIMARY EFFICACY ENDPOINT

For the time to confirmed clinical recovery (days) through Day 29, without re-hospitalization through Day 29, missing ordinal scale for clinical severity scores and missing hospitalization data will not be imputed before applying the censoring rules for the main analysis of the primary efficacy endpoint (refer to Section 16.1.1).

[figure not shown]

Additionally, a Cox proportional hazards model will be performed including the baseline clinical severity of 2 on the 8-point ordinal scale (yes or no) stratification variable, remdesivir use at baseline (yes or no) stratification variable, both as captured on the IWRS, country (region), and treatment arm as factors. Ties will be handled using the exact

method. The HR (candidate agent plus SoC vs. placebo plus SoC) and corresponding two-sided 95% CI will be provided.

For the methods to control the overall alpha level of a sub-protocol at the two-sided 0.05 level, refer to Section 7.4.

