7.6. ADJUSTMENTS FOR COVARIATES AND FACTORS TO BE INCLUDED IN ANALYSES

The analyses will be adjusted for the following covariates and factors. For details of their inclusion in the models, refer to Sections 16.1.3, 16.2.3, and 16.3.3.

- Baseline value of the concerned endpoint, when applicable;

CCI [Redacted]	[Redacted]	Version Number:	Amendment 1, v1.0
PPD [Redacted]	[Redacted]	Version Date:	23Apr2021
CCI [Redacted]	[Redacted]	[Redacted]	[Redacted]
[Redacted]	[Redacted]	[Redacted]	[Redacted]
[Redacted]	[Redacted]	[Redacted]	[Redacted]

- Baseline clinical severity score of 2 randomization strata (yes or no), as captured on the IWRS;
- Remdesivir at baseline randomization strata (yes or no), as captured on the IWRS;
- Country (or region; refer to Section 7.5).

Sensitivity analyses replacing the randomization strata as captured in IWRS by the randomization strata as derived based on the data captured on the electronic case report form (eCRF) might be performed if at least 10% of the patients are mis-stratified at the time of randomization for a stratification variable (refer to Section 16.1.4) i.e.,

- Baseline clinical severity score of 2 (yes or no) as captured on the *Ordinal Scale for Clinical Severity* page of the eCRF;
- Remdesivir use at baseline (yes or no) based on data collected on the *Concomitant Medications* page of the eCRF (i.e., medications that were taken by a patient on the day the patient was randomized to a sub-protocol).

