7.7. EXAMINATION OF SUBGROUPS

Subgroup analyses will be conducted as supplementary analyses for the primary and key secondary efficacy endpoints as stated in Sections 16.1.5 and 16.2.5, respectively.

The subgroups are:

- Age (years) at informed consent ($\geq 18 - \leq 49$, $\geq 50 - \leq 64$; $\geq 65 - \leq 84$ or ≥ 85);
- Sex (male or female);
- Race (White, Black or African American or Other);
- Ethnicity (Hispanic or Latino or not Hispanic or Latino);
- Country (or region; refer to Section 7.5);
- Obesity co-morbidity at screening ($BMI < 30 \text{ kg/m}^2$ or $BMI \geq 30 \text{ kg/m}^2$);
- Diabetes co-morbidity at screening (yes or no);
- Cardiovascular disease co-morbidity at screening (yes or no);
- Hypertension co-morbidity at screening (yes or no);

CCI

PPD

Version Number: Amendment 1, v1.0
Version Date: 23Apr2021

CCI

Master Statistical Analysis Plan

- Chronic lung disease co-morbidity at screening (yes or no);
- Chronic liver disease co-morbidity at screening (yes or no);
- Kidney disease co-morbidity at screening (yes or no);
- Immunosuppressive/Immunocompromise disorder co-morbidity at screening (yes or no);
- Time since hospital admission (≤ 5 days or > 5 days; refer to Section 11.1);
- Baseline clinical severity score of 2 randomization strata (yes or no) as captured on the IWRS;
- Disease severity at baseline (2, 3, 4, or 5) based on the ordinal scale for clinical severity as captured on the *Ordinal Scale for Clinical Severity* page on the eCRF;
- Disease severity score of 2, 3 or 4 (yes or no) at baseline based on the ordinal scale for clinical severity as captured on the *Ordinal Scale for Clinical Severity* page on the eCRF
- Remdesivir use at baseline randomization strata (yes or no) as captured on the IWRS;
- Concomitant use of remdesivir at any time during the period of the endpoint of interest (yes or no) based on collected on the *Concomitant Medications* page of the eCRF (for concomitant use definition, refer to Section 13). The concomitant use of remdesivir at any time during the period of the endpoint of interest in the ‘yes’ subgroup will be further broken down by duration of concomitant use of remdesivir, where the duration of concomitant use categories (e.g., $< x$ days or $\geq x$ days) will be determined in a blinded fashion based on emerging data before the interim database lock of a candidate agent primary analysis;

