For the disease severity at baseline subgroups, if data are too sparse for the subgroups of patients with a disease severity at baseline of 3 or 4 (i.e., less than 10% of FAS patients, regardless of the treatment arm), these two subgroups will be pooled together. If data are too sparse for the subgroup of patients with a disease severity at baseline of 2, pooled 3/4 (if applicable) or 5, only descriptive statistics will be provided for the concerned subgroups. That is, the subgroup of patients with a disease severity at baseline of 2 or 5 will not be pooled with any other subgroup.

For any other subgroups, if data are too sparse (i.e., less than 10% of FAS patients for a subgroup, regardless of the treatment arm), only descriptive statistics will be provided for the concerned subgroups.

Additional subgroups might be defined based on emerging data to explore the impact of medical therapy in COVID-19 with proven efficacy (e.g., vaccine use, other evolving SoC, etc.). The decision to add such subgroups and their definition will be taken in a blinded fashion before the interim database lock of a candidate agent primary analysis based on data captured on the *Concomitant Medications* page of the eCRF.

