CCI [Redacted]

as suggested in Lipkovich et al, 2016, will be used as the imputation method separately for each treatment arm. For each sub-protocol, the prior distribution and pieces used in this covariates-adjusted and delta-adjusted piecewise exponential survival model will be determined in a blinded fashion prior to the DBL for a sub-protocol Primary Analysis. The model will include the baseline clinical severity of 2 on the 8-point ordinal scale stratification variable (yes or no), remdesivir use at baseline stratification variable (yes or no), both as captured on the IWRS, and country (region; refer to Section 7.5) as covariates.

If the imputed event time exceeds Day 29, the patient will be censored at Day 29. Multiple imputation (MI) method will be used where 100 imputed datasets will be generated using above model and a seed of 2102.

Each of the multiply-imputed datasets will then be analyzed using the same stratified log-rank test and Cox regression model as for the main analysis to the primary efficacy endpoint (refer to Section 16.1.3). The survival distribution quartiles (25th, 50th [median], and 75th percentiles), log-rank statistics, and hazard ratios will be combined as suggested in Moscovici and Ratitch, 2017. The combined statistics and p-value associated with the combined log-rank statistic will be presented.

[figure not shown]
A tipping point analysis will be implemented where the above described MI will first be performed using a $\delta = 0.95$ for the candidate agent plus SoC treatment arm and then repeated but decreasing the δ -adjustment applied to the candidate agent plus SoC treatment arm gradually by reduction of 0.05 (i.e., 0.95, 0.90, 0.85, etc.) until the study conclusion is not significant anymore. For each of these analyses, the δ used for the concurrent shared placebo plus SoC control arm will always remain 1. The δ when the study conclusion becomes non-significant will be referred to as the tipping point.

Additional sensitivity analyses might be specified in the sub-protocol SAPs.

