16.2.3.1. Binary Endpoints

For the incidence of patients with oxygen-free recovery at Day 29 (refer to Section 16.2.1.1), incidence of patients with ≥ 2 -point improvement from baseline or fit for discharge on the ordinal scale at Day 29 (refer to Section 16.2.1.2), incidence of all-cause mortality through Day 29 (refer to Section 16.2.1.3), incidence of patients with clinical recovery at Days 8, 15 and 29 (refer to Section 16.2.1.8), and incidence of patients with sustained clinical recovery as confirmed by Day 60 follow-up (refer to Section 16.2.1.9), the number and percentage of patients with and without the event will be provided by treatment arm. For the incidence of all-cause mortality, primary reason of death will also be summarized by treatment arm.

For each of these endpoints, a logistic regression will be performed to test the difference between a candidate agent plus SoC and placebo plus SoC treatment arms, including the baseline clinical severity of 2 on the 8-point ordinal

scale for clinical severity (yes or no) stratification variable, remdesivir use at baseline (yes or no) stratification variable, both as captured on the IWRS, country (region; refer to Section 7.5), and treatment arm as factors. The estimate of the relative risk (risk difference) between the two treatment arms, the corresponding two-sided 95% Wald CI, and the p-value obtained from the logistic regression model will be provided.

The odds ratio (of candidate agent plus SoC vs. placebo plus SoC) for having the event at the specified Day and its two-sided 95% CI will also be presented.

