16.2.3.2. Ordinal Endpoints

For the incidence of patients in each category of the 8-point ordinal scale for clinical severity at Days 8, 15, and 29 endpoints (refer to Section 16.2.1.4), the number and percentage of patients in each ordinal scale category will be provided at each specified Day for each treatment arm and will be analyzed using a proportional odds model, including the baseline clinical severity of 2 on the 8-point ordinal scale for clinical severity (yes or no) stratification variable, remdesivir use at baseline (yes or no) stratification variable, both as captured on the IWRS, country (region; refer to Section 7.5), and treatment arm as factors.

The odds ratio (candidate agent plus SoC vs. placebo plus SoC) of having a higher score than any given category *k* of the ordinal scale at Days 8, 15, and 29, their two-sided 95% CI, and associated p-value will be presented for each specified Day, where it is assumed that the odds ratio does not differ depending upon *k*.

[figure not shown]
The worst post-baseline score on the 8-point ordinal scale for clinical severity from randomization to Day 29 (refer to Section 16.2.1.5) and each “number of days” endpoint (refer to Sections 16.2.1.6 and 16.2.1.7) will be summarized and analyzed similarly.

Shift tables from baseline to each post-baseline day up to Day 29 as well as to the worst post-baseline score will also be provided for the 8-point ordinal scale for clinical severity.

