16.2.4. SENSITIVITY ANALYSES FOR SECONDARY EFFICACY ENDPOINTS

The following sensitivity analyses to the main analysis of each key secondary efficacy endpoint will be performed. No sensitivity analyses will be performed for the non-key secondary efficacy endpoints.

- **Sensitivity to stratification variables:** The main analysis of each key secondary efficacy endpoint will be repeated but the stratification variables as derived based on the eCRF data (refer to Section 7.6) will be included in the model instead of the stratification variables as captured on the IWRS if at least 10% of patients are mis-

stratified at the time of randomization for a stratification variable.

• **Sensitivity analysis to missing data assumption #1:**

- For the incidence of patients with oxygen-free recovery at Day 29 (refer to Section 16.2.1.1), a multiple imputation approach will be applied to impute the missing oxygen-free recovery status (yes or no) at Day 29 for subjects who discontinued from study before or on Day 29 using a logistic regression including effects for the treatment arm, baseline clinical severity of 2 on the 8-point ordinal scale for clinical severity stratification variable (yes or no), remdesivir use at baseline stratification variable (yes or no), both as captured on the IWRS, and country (or region; refer to Section 7.5). One hundred (100) imputed datasets will be generated using a seed of 2504.

Each imputed dataset will then be analyzed using the same model as for the main analysis of this key secondary efficacy endpoint (refer to Section 16.2.3.1).

The relative risks and parameter estimates for the effects of the logistic regression model and their SEs will then be combined using the Rubin’s rule to obtain a combined estimate of the treatment arm effect and its SE, and the associated p-value will be provided. The relative risks and odds ratios will first be log transformed and then combined to obtain a combined relative risk and combined odds ratio, and their associated 95% CI. The combined relative risk and combined odds ratio, and associated 95% CI, will be back-transformed before being displayed;

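### The models for two key secondary endpoints and the ordinal scale pool baseline scores 3, 4 and 5, although the full score is collected; using it could add a little power and would leave the decision test unchanged

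*SAP*

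**What the plan says.** Three sets of efficacy models in the Master SAP carry baseline severity only as the IWRS randomization stratum, score 2 yes or no, next to remdesivir use and country or region:

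- Cox model for the primary endpoint (16.1.3): "a Cox proportional hazards model will be performed including the baseline clinical severity of 2 on the 8-point ordinal scale (yes or no").
- Logistic models for the binary endpoints, including all three key secondary endpoints (16.2.3.1): "including the baseline clinical severity of 2 on the 8-point ordinal" scale.
- Proportional-odds models (16.2.3.2): the categories "will be analyzed using a proportional odds model, including the baseline clinical severity of 2 on the 8-point ordinal scale", again yes or no.

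The imputation models keep the same term. Section 16.1.4 states "The model will include the baseline clinical severity of 2 on the 8-point ordinal scale stratification variable (yes or no"), and 16.2.4 imputes "using a logistic regression including effects for the treatment arm, baseline clinical severity of 2 on the 8-point ordinal scale". The mortality Cox models in 16.2.5 and 16.4.5 use it as well.

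The full score is available. Section 11 tabulates it by arm, and 7.7 defines a subgroup as "Disease severity at baseline (2, 3, 4, or 5) based on the ordinal scale for clinical severity as captured on the" eCRF page. Section 7.6 lists "Baseline value of the concerned endpoint, when applicable" among the covariates but refers to 16.1.3, 16.2.3 and 16.3.3 for detail. The first two name no baseline score, and the exploratory section is redacted. Master Protocol 4.1 stratifies randomization by score 2 yes/no and remdesivir, so allocation is not balanced within scores 3 to 5.

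**The concern.** Master Protocol Table 2 separates score 3 (noninvasive ventilation or high-flow oxygen), score 4 (low-flow oxygen) and score 5 (no oxygen). If these groups recover at different rates, a model that treats them as one level leaves explainable variation in the outcome. Two things follow. Some power on the key secondary tests goes unused, and the reported hazard ratio and odds ratios move with any chance imbalance in 3/4/5 between the arms.

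No planned analysis fills the gap. The eCRF-based sensitivity analysis keeps the dichotomy and depends on at least 10% of patients being mis-stratified. The subgroup analyses give effects within each score, not one overall effect adjusted for it.

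The point matters for COV-01-004, whose SAP takes its efficacy analyses from the Master SAP. The COV-01-001 and COV-01-005 SAPs have dropped efficacy inference.

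**Working it through.** **The plan's own figures reproduce.** With 490 events, HR 1.364 and one-sided 0.025, fixed-design power is Φ(√490/2 × ln 1.364 − 1.96) = Φ(11.07 × 0.3104 − 1.96) = Φ(1.476) = 93.0%. With the two futility boundaries treated as binding it is 88.3%, the stated figure. For 350 per arm the two-proportion formula gives 80.0% (65 to 74.7%), 80.0% (70 to 79.2%) and 79.7% (15 to 8.25%), against a stated 80%. None of these figures is disputed.

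**Assumptions.** The documents give neither the score mix nor prognosis by score. Assumed: mix 2/3/4/5 = 10/25/50/15%, 350 per arm, and remdesivir and five regions non-prognostic. Log-odds by score 2/3/4/5 for the logistic models:

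- alike: −1.5/0/0/0
- mild: −1.5/−0.3/0/0.15
- moderate: −1.5/−0.8/0/0.6
- strong: −2/−1.5/0/1

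Signs are reversed for death. Each cell has 6,000 simulated trials (SE about 0.5 point). The four-level model returned to the score-2 term when any level had fewer than 5 events or non-events.

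**Power, score-2 term → four levels (%)**

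| Endpoint | Alike | Mild | Moderate | Strong |
|---|---|---|---|---|
| Oxygen-free recovery | 81.4 → 81.5 | 82.6 → 82.8 | 82.2 → 83.6 | 82.3 → 86.5 |
| 2-point or fit for discharge | 82.1 → 82.2 | 82.2 → 82.5 | 82.4 → 83.8 | 82.6 → 85.3 |
| Mortality | 81.4 → 81.3 | 81.7 → 81.7 | 80.7 → 81.1 | 81.6 → 81.8 |

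The oxygen-free gain is therefore 0.1, 0.2, 1.4 and 4.2 points. Type I error, score-2 then four levels, is 5.3 and 5.4% (oxygen-free), 5.0 and 5.2% (2-point) and 5.1 and 5.1% (death).

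**The 2-point row is optimistic.** Under Master SAP 16.2.1.2, a patient at baseline 2 succeeds at score 4 and one at baseline 3 succeeds at score 5, while baseline 4 or 5 needs score 6. The lower bar should flatten the gradient. In a separate, simpler run, the score-3 log-odds was halved and the score-2 log-odds cut by about a third. The gain fell from 1.6 to 0.6 points (moderate) and from 4.1 to 1.2 (strong).

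**Mortality.** In the strong case 2.35 deaths are expected at score 5. The chance of none is about exp(−2.35) = 9.5%, and then there is no finite score-5 estimate. Without a fallback, power drops to 75.7%.

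**Chance imbalance and the hazard ratio.** Each arm has about 0.90 × 350 = 315 patients at scores 3 to 5, of whom 25/90 = 27.8% are at score 3. The SD of the difference in score-3 counts is √(2 × 315 × 0.278 × 0.722) = 11.2. Five points is 17.5 patients, and 17.5/11.2 = 1.56, so the chance is about 6% in each direction.

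The survival runs used 4,000 trials per cell, a conditional HR of 1.364 and moderate recovery hazards 0.25/0.5/1/1.5. With 5 points more score 3 (in place of 4) in the active arm, the score-2 HR averages 1.29. With 5 points fewer it averages 1.39. The four-level HR is 1.37 in both. The same-trial ratio of the two HRs (5th to 95th percentile) is 0.99 to 1.01 when scores 3 to 5 recover alike and 0.92 to 1.04 in the moderate case.

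**Effect on agreement with the log-rank.** If the four-level Cox model became the main one, its interval would exclude 1 while the planned log-rank was not significant in 6.8% of trials instead of 2.4% (moderate), or 10.3% instead of 2.1% (strong).

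**Limits.** The survival runs do not model deaths or futility looks and use Efron ties where the SAP uses exact. The proportional-odds models were not simulated.

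**The case against.** The strongest case for leaving the plan alone is that it adjusts for the randomization factors, as the protocol specifies, with nominal type I error. The 2/3/4/5 distribution will be shown by arm, so an imbalance would be visible. The gains rest on assumed gradients and are trivial in the mild case. Key secondary endpoints are formally tested only after the primary succeeds (Master SAP 7.4), so these powers are marginal and overstate the gain within the testing sequence.

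Much of this stands, and it limits the remedy. Mortality gains nothing and may have too few score-5 deaths. Replacing the main Cox term would make the interval and the decision p-value disagree more often. A table of the imbalance, however, does not give an overall effect adjusted for it.

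A reader might infer that the reported hazard ratio is biased because its mean rises from 1.338 to 1.369 in the moderate case. Most of that shift is non-collapsibility: the four-level ratio is conditional on finer severity. A reader might also infer that the primary power statement is wrong, but it reproduces.

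**Conclusion.** This is an improvement to consider, not an error. The models are valid as written, and the documents do not support reading them as biased or as inflating type I error. What holds is narrower: data already collected would allow a somewhat more efficient analysis of two key secondary endpoints and the ordinal scale, and would show how far a chance imbalance in scores 3 to 5 moves the primary hazard ratio.

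Under the assumed mix and gradients the gain is about 0 to 4 points of power for oxygen-free recovery. With a flattened gradient it is about 0.6 to 1.2 points (moderate to strong) for the 2-point endpoint. There is none if scores 3 to 5 recover alike, and none was found for mortality. For the proportional-odds models the case rests on reasoning alone: Section 7.6 lists the baseline value of the endpoint, and for the ordinal scale that value exists. Confidence in the description is high; confidence in the size is moderate, because the documents cannot supply it.

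**What to change.** Record the following in Master SAP 3.3 for COV-01-004, while blinded and before its first database lock for an interim or primary analysis.

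1. **Two key secondary endpoints and the ordinal scale.** Use the pre-dose eCRF score as a factor (2, 3, 4, 5) in place of score 2 yes/no, keeping remdesivir and country or region. This applies to the logistic models for oxygen-free recovery and for 2-point improvement or fit for discharge, and to the proportional-odds models for the score at Days 8, 15 and 29 and the worst score. Carry the factor into the matching imputation models in 16.2.4.
2. **Rules fixed in advance.** Pool 3 with 4 if either is below 10%, in line with 7.7 ("if data are too sparse for the subgroups of patients with a disease severity at baseline of 3 or 4"). Return to the score-2 term if level 3, 4 or 5 has fewer than 5 events or non-events, counted over both arms. If the eCRF score is missing, use the IWRS stratum and the last available pre-dose information. Keep the IWRS score-2 models as sensitivity analyses.
3. **Mortality.** Keep the score-2 term in the logistic model and in the Cox models of 16.2.5 and 16.4.5.
4. **Primary endpoint.** State that the planned stratified log-rank is the only decision test and that the score-2 Cox hazard ratio is its matching estimate. Add to 16.1.5 a supplementary Cox model with the four-level score and a supplementary log-rank stratified by score and remdesivir.
5. **Consistency.** Reconcile 7.6 with 16.1.3 and 16.2.3.

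No new data are needed. The costs are SAP text, alignment of the covariate wording in Master Protocol 9.3.2, 9.3.3 and the synopsis (possibly by amendment, with the approvals that requires), and odds ratios that become conditional on finer severity. Blinded choice of model factors before lock has a precedent in 7.5, for country or region.

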16.1.4. SENSITIVITY ANALYSES FOR PRIMARY EFFICACY ENDPOINT

The following sensitivity analyses to the main analysis of the primary efficacy endpoint will be performed:

- **Sensitivity to stratification variables:** The main analysis to the primary efficacy endpoint (refer to Section 16.1.3) may be repeated but stratification variables as derived based on the eCRF data (refer to Section 7.6) will be included in the model instead of the stratification variables as captured on the IWRS. This analysis will be performed only if at least 10% of patients are mis-stratified at the time of randomization for a stratification variable;
- **Sensitivity to censoring assumptions #1:** The main analysis of the primary efficacy endpoint will be repeated but patients who discontinued early from the study before or on Day 29 will be censored at Day 29;
- **Sensitivity to censoring assumptions #2:** The main analysis of the primary efficacy endpoint will be repeated but, for patients who discontinued early from the study before or on Day 29, the last patients' known event status will be carried forward to Day 29 before applying the censoring rules for the main analysis of the primary efficacy endpoint (refer to Section 16.1.1).
- **Sensitivity to censoring assumptions #3:** The primary analysis assumes that censoring is at random (CAR) for patients who discontinued early from the study before or on Day 29 (refer to Section 16.1.3). For this sensitivity analysis, the time to event (refer to Section 16.1.1) will be imputed only for these patients using a model that assumes censoring not at random (CNAR). The model will assume that these patients would have hazard following discontinuation from study that is reduced by some factor delta (δ) compared with hazard of remaining patients in their group who have similar key baseline characteristics (Lipkovich et al, 2016), where reduced hazard rate indicates a longer time to event (confirmed clinical recovery through Day 29, without re-hospitalization through Day 29). In order to stress-test the assumption of CAR with an assumption that is less favorable to a candidate agent plus SoC treatment arm, a $\delta < 1$ will be used for the candidate agent plus SoC treatment arm while a $\delta = 1$ will be used for the concurrent shared placebo plus SoC control arm as $\delta = 1$, which corresponds to the CAR assumption.

Multiple imputation method using covariates-adjusted and delta-adjusted piecewise exponential survival model

CCI [Redacted]

as suggested in Lipkovich et al, 2016, will be used as the imputation method separately for each treatment arm. For each sub-protocol, the prior distribution and pieces used in this covariates-adjusted and delta-adjusted piecewise exponential survival model will be determined in a blinded fashion prior to the DBL for a sub-protocol Primary Analysis. The model will include the baseline clinical severity of 2 on the 8-point ordinal scale stratification variable (yes or no), remdesivir use at baseline stratification variable (yes or no), both as captured on the IWRS, and country (region; refer to Section 7.5) as covariates.

If the imputed event time exceeds Day 29, the patient will be censored at Day 29. Multiple imputation (MI) method will be used where 100 imputed datasets will be generated using above model and a seed of 2102.

Each of the multiply-imputed datasets will then be analyzed using the same stratified log-rank test and Cox regression model as for the main analysis to the primary efficacy endpoint (refer to Section 16.1.3). The survival distribution quartiles (25th, 50th [median], and 75th percentiles), log-rank statistics, and hazard ratios will be combined as suggested in Moscovici and Ratitch, 2017. The combined statistics and p-value associated with the combined log-rank statistic will be presented.

[figure not shown]
A tipping point analysis will be implemented where the above described MI will first be performed using a $\delta = 0.95$ for the candidate agent plus SoC treatment arm and then repeated but decreasing the δ -adjustment applied to the candidate agent plus SoC treatment arm gradually by reduction of 0.05 (i.e., 0.95, 0.90, 0.85, etc.) until the study conclusion is not significant anymore. For each of these analyses, the δ used for the concurrent shared placebo plus SoC control arm will always remain 1. The δ when the study conclusion becomes non-significant will be referred to as the tipping point.

Additional sensitivity analyses might be specified in the sub-protocol SAPs.

